Pregnancy: For approved indications, the fluconazole dosage used in this protocol is classified as category D risk for pregnant females. Category D risk indicates there is positive evidence of human fetal risk, including increased risk or rates of miscarriages, based on adverse reaction data from investigational or marketing experience or studies in humans. However, potential benefits may warrant use of the drug in pregnant women despite potential risks. A few published case reports describe a rare pattern of distinct congenital anomalies in human infants exposed in utero to doses between 400-800 mg/day of fluconazole. The risk benefit ratio for fluconazole when used in this protocol is still unknown, thus pregnant women will be excluded from participating in this study. In addition, pregnancy testing will be performed in all women of childbearing potential prior to randomization and throughout the duration of the study intervention. All women of childbearing potential will be required to use a highly effective method of birth

control. Any pregnancy will be cause for discontinuation of active treatment and will be followed for up to two months after birth to assess for potential adverse effects to the fetus.

Other unknown risks, discomforts, or side effects: There is a theoretical risk that early treatment may modify the host response and that treatment will impair host control and may lead to more relapses after treatment is eventually stopped.

Electrocardiogram (ECG): Mild skin irritation from the application and/or removal of the ECG patches is possible.

Blood sampling: Drawing blood may cause transient discomfort and fainting. Fainting is usually transient and managed by having the subject lie down. Bruising at the blood draw site may occur, but can be prevented or lessened by applying pressure to the draw site for several minutes.

Drawing blood may also cause infection. The use of aseptic technique will make infection at the site where blood will be drawn extremely unlikely.

Nasopharyngeal swab: Side effects of collecting a nasal pharyngeal swab may include mild discomfort and/or irritation of the nasal passage, occasional gagging, and rarely bleeding of the nasal passage.

Throat swab: Side effects of collecting a throat swab may include mild discomfort and/or irritation of the throat passage and occasional gagging.

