5. STUDY ENROLLMENT AND WITHDRAWAL

5.1. Subject Inclusion Criteria

Subjects eligible to participate in this study must meet all of the following inclusion criteria:

1. Aged ≥ 18 years and presenting for clinical care in coccidioidomycosis endemic areas.
2. Have a health care provider who has decided to treat community acquired pneumonia with antibacterials.
3. Be able to take and tolerate oral antibacterials/antifungals.
4. Able to understand the study and provide informed consent.
5. Willing and able to comply with study procedures and complete study visits.
6. Willing to allow access to medical records, and medical records are available to the study team.
7. The first dosage of study drug will be administered within 72 hours of presentation for care.
8. Able to swallow large pills.
9. Sexually active female subjects must be of non-childbearing potential* or, if of childbearing potential, must use a highly effective method of birth control**(captured on the appropriate data collection form)

*Non-childbearing potential is defined as being post-menopausal for at least 18 months or surgically sterile via bilateral oophorectomy or hysterectomy.

**Female subjects must avoid becoming pregnant by using one of the following acceptable methods of birth control for 30 days prior to study drug dosing and must be maintained for 30 days after last dose of study drug:

- a. Intrauterine contraceptive device; OR
 - b. Oral contraceptives; OR
 - c. Implanon®, Nexplanon®, DepoProvera®, contraceptive skin patch or NuvaRing®; OR
 - d. Tubal ligation; OR
 - e. Exclusively same-sex relationships
10. Non-pregnant female subjects of childbearing potential must have a negative pregnancy test within 24 hours prior to enrollment and at Visits 02 - 03.
 11. Subjects receiving any of the drugs reported to have manageable drug interactions with fluconazole (see section 6.6.2: Drug Interactions with Fluconazole) are allowed to be enrolled based on PI clinical judgment.

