(Window: Day 48 to Day 51)

Follow-up and additional procedures will vary according to randomization group and Coccidioidomycosis status.

Coccidioidomycosis Negative Subjects Who Received Fluconazole

- Subjects will be reminded that they they did not meet the protocol defined case definition of CAP caused by acute coccidioidomycosis infection.
- Subjects who were randomized to fluconazole will be queried for SAE collection and referred to their health care provider with results of the safety lab testing for follow-up if abnormalities are noted.
- Remind subject that contraceptives must be maintained until 30 days after the last dose of study medication.

-
- Those subjects who did not meet the protocol defined case definition of CAP caused by acute coccidioidomycosis infection will be dismissed from the study following data collection and referral.

Coccidioidomycosis Positive Subjects Who Received Fluconazole

- Subjects will be reminded that they met the protocol defined case definition of CAP caused by acute coccidioidomycosis infection.
- Subjects who were randomized to fluconazole will be queried for SAE collection and referred to their health care provider with results of the safety lab testing for follow-up if abnormalities are noted.
- Remind subject that contraceptives must be maintained until 30 days after the last dose of study medication.
- Refer subject to their identified health care provider with for evaluation of need for continued treatment and clinical follow-up.

7.3.5. Follow-up Visit 06 (Day 90): Telephone Follow-up for Coccidioidomycosis Positive Subjects Only

(Window: Day 83 to Day 97)

- Complete PROMIS Item Bank v2.0 - Ability to Participate in Social Roles and Activities - Short Form 4a
- Complete SF-12v2
- Instruct subject to complete Extra-Pulmonary Symptom Score and remind subject to mail results to study team.
- Interview the subject and review the subject's medical record for diagnosis of disseminated coccidioidomycosis
- Refer subject to their identified health care provider for clinical follow-up of any ongoing health concerns identified during interview or completion of patient reported outcome measures.

7.3.6. Follow-up Visit 07 (Day 180): Telephone Follow-up for Coccidioidomycosis Positive Subjects Only

(Window: Day 173 to Day 187)

- Complete PROMIS Item Bank v2.0 - Ability to Participate in Social Roles and Activities - Short Form 4a
- Complete SF-12v2

-

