9. ASSESSMENT OF SAFETY

9.1. Specification of Safety Parameters

Fluconazole is an approved drug with an established and well-described safety profile. The most prevalent of the drug side effects include headache (13%), nausea (7%), and abdominal pain (6%). In less than 1% of individuals taking this medication there is a perversion of taste. There are rare reports of exfoliative dermatitis, some of which were fatal. There are reports of liver toxicity (in particular with patients with co-morbidities and previous liver injury), which are not dose dependent.

As fluconazole is an approved drug with a long prescribing history, NIAID does not expect that any new drug related safety signal will be detected in this trial. As such, the safety data collection will be targeted to only collect Suspected Unexpected Serious Adverse Reactions (SUSARs) and congenital anomalies/birth defects.

For individual patients, liver function testing will be performed to monitor for possible liver injury.

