9.2.2. Serious Adverse Events

Serious Adverse Event (SAE): An adverse event or suspected adverse reaction is considered “serious” if, in the view of either the investigator or sponsor, it results in any of the following outcomes:

- Death
- A life-threatening adverse event*
- Inpatient hospitalization or prolongation of existing hospitalization
- A persistent or significant incapacity or substantial disruption of the ability to conduct normal life functions, or
- A congenital anomaly/birth defect
- Important medical events that may not result in death, be life-threatening, or require hospitalizations may be considered serious when, based upon appropriate medical judgment they may jeopardize the patient or subject and may require medical or surgical intervention to prevent one of the outcomes listed in this definition. Examples of such medical events include allergic bronchospasm requiring intensive treatment in an emergency room or at home, blood dyscrasias or convulsions that do not result in inpatient hospitalization, or the development of drug dependency or drug abuse

*Life-threatening adverse event. An adverse event is considered “life-threatening” if, in the view of either the site principal investigator or sponsor, its occurrence places the patient or subject at immediate risk of death. It does not include an adverse event that, had it occurred in a more severe form, might have caused death.

Death and life-threatening events are part of the efficacy endpoints of this trial and will not be reported or collected as SAEs unless they meet the criteria below.

Only the following events will be considered SAEs:

- Congenital anomalies or birth defect, OR
- Any condition that meets the regulatory definition of a SAE AND is unexpected (per PI) AND is suspected to be directly caused by the study drug (e.g., anaphylaxis, Stevens-Johnson syndrome, exfoliative dermatitis)

Protocol defined SAEs will be:

- Collected from the time of enrollment through visit Day 49
- Assessed for relationship to study product
- Recorded on the appropriate SAE form and eCRF
- Followed through resolution by a licensed study physician listed on the Form FDA 1572 as the site principal investigator or sub-investigator
- Reviewed and evaluated by DMID, the DSMB (periodic review), and the IRB

9.2.3. Procedures to be Followed in the Event of Abnormal Laboratory Test Values or Abnormal Clinical Findings

Study drug will be stopped for the individual subject if:

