9.3.3. Reporting of Pregnancy

Although not AEs, pregnancies are reportable events. Any pregnancies that occur during the study period in women who have received any study product (fluconazole or placebo) will be reported via the AdvantageEDC on the Pregnancy Report form within 5 days of site awareness. The report will include pregnancy outcome (e.g., any premature terminations, elective or therapeutic, any spontaneous abortions or stillbirths), as well as the health status of the mother and child, including date of delivery and infant’s sex and weight. Pregnancies will be followed up to two months after birth. All pregnancies will be reported to the clinical data management group. If the database is locked at time of pregnancy, a supplemental report will be generated and completed after birth and follow-up, which will be appended to the database.

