9.4. Type and Duration of Follow-up of Subjects after Adverse Events

SAEs will be followed from the time of enrollment until completion of study even if this extends beyond the study-reporting period. For those subjects who are dismissed from study follow-up after study Day 43 (Visit 04), SAEs will be followed but new SAEs will not be collected. All subjects who received fluconazole will be followed through Day 49. Resolution of an SAE is defined as the return to pretreatment status or stabilization of the condition with the expectation that it will remain chronic.

Follow-up procedures, evaluations, and outcomes will be recorded on the appropriate data collection form.

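### Congenital anomaly is one of only two protocol-defined SAE types, but SAE collection stops at Day 49, before any birth from an on-study conception, and the pregnancy-reporting period is not defined

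*Combined protocol and SAP*

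**What the plan says.** **SAE definition and window.** Section 9.1 limits safety collection: the trial will "only collect Suspected Unexpected Serious Adverse Reactions (SUSARs) and congenital anomalies/birth defects". Section 9.2.2 then names only two SAE types. The first is "Congenital anomalies or birth defect, OR"; the second is a serious, unexpected event suspected to be caused by study drug. The unexpectedness and causality conditions attach to the second type only. Protocol-defined SAEs are "Collected from the time of enrollment through visit Day 49", and section 4 repeats the Day 49 limit. For subjects dismissed after Day 43, section 9.4 adds that "SAEs will be followed but new SAEs will not be collected".

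**Fetal risk and contraception.** Section 2.3.1 classes the protocol dosage as Category D in pregnancy: "Category D risk indicates there is positive evidence of human fetal risk, including increased risk or rates of miscarriages". Under inclusion criterion 9 in section 5.1, birth control "must be maintained for 30 days after last dose of study drug". The instruction for fluconazole recipients at Visit 04 (section 7.3.3) is "Remind subject that contraceptives must be maintained until 30 days after the last dose of study medication", and section 7.3.4 repeats it at the Day 49 call.

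**Pregnancy reporting.** Section 9.3.3 says: "Any pregnancies that occur during the study period in women who have received any study product (fluconazole or placebo) will be reported". Reports go on a Pregnancy Report form within 5 days of site awareness. They cover the pregnancy outcome and the health of mother and child, with follow-up to two months after birth. A supplemental report is appended if the database is already locked when the pregnancy occurs.

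**Late SAEs and analysis.** Section 9.3.1 also requires a report, at any time after study completion, of an SAE that the investigator learns of and that is suspected to be related. Section 11.4.3 bases the safety analysis on SAEs as section 9.2.2 defines them and does not mention pregnancy outcomes.

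**The concern.** Two things do not fit together.

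First, a fixed study-day cut-off suits acute reactions such as anaphylaxis. It does not suit an outcome normally seen at the end of a pregnancy. The SAE rule names the event and then closes before the event can occur. The information would arrive by another route, but that route leads to a different form, a different reporting deadline (5 days rather than 24 hours) and no stated place in the analysis. The post-study SAE route in section 9.3.1 requires suspected relatedness, a condition that section 9.2.2 does not set for anomalies.

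Second, the protocol asks women to avoid conception until 30 days after the last dose but sets no matching period for finding out whether conception occurred. Everything in section 9.3.3 depends on the pregnancy being reported, and the period in which it must be reported is not stated in days.

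At stake is complete, by-arm reporting of one of the few safety outcomes that this trial collects. No efficacy endpoint is affected.

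**Working it through.** There is no plan figure to reproduce. The check is date arithmetic on the protocol's study days.

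**Inputs from the protocol**
- Last dose: about Day 42 (section 6.2, at least 42 days of dosing). Visit 04 may fall from Day 42 to Day 46 (section 7.3.3).
- Contraception: 30 days after last dose (section 5.1).
- Last scheduled pregnancy test: Day 43 (section 7.3.3, Table 12).
- Last contact: Day 49, window Day 48 to 51, for fluconazole recipients not meeting the case definition; Day 43 for placebo recipients not meeting it (sections 4, 7.3.3, 7.3.4).
- Negative pregnancy test before enrolment (section 5.1).

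**Assumptions, not in the protocol**
- Conception to term birth: 266 days, with 154 days as an early-preterm bound.
- A test turns positive 10 to 14 days after conception (range 7 to 21).

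**Step 1. Can a birth fall inside the SAE window?** Birth day = conception day + 266 (or + 154).
- Conception on Day 1: term birth at 1 + 266 = Day 267; early bound 1 + 154 = Day 155.
- Conception on Day 42: term birth at 42 + 266 = Day 308; early bound 42 + 154 = Day 196.

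The earliest of these, Day 155, is 155 − 49 = 106 days after the SAE cut-off. The conclusion does not depend on the exact gestation assumed.

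**Step 2. Would the pregnancy follow-up reach the birth?** Taking two months as 60 days, follow-up ends at 267 + 60 = Day 327 to 308 + 60 = Day 368. Section 9.3.3 covers this for any reported pregnancy.

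**Step 3. How much of the contraception period has scheduled contact?** Contraception end = last dose day + 30.

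| Last dose | Contraception ends | Last contact | Days after last contact |
|---|---|---|---|
| Day 42 | Day 72 | Day 49 | 72 − 49 = 23 of 30 |
| Day 42 | Day 72 | Day 48 to 51 (call window) | 24 to 21 of 30 |
| Day 46 | Day 76 | Day 49 | 76 − 49 = 27 of 30 |

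Placebo recipients without coccidioidomycosis leave at Day 43, 72 − 43 = 29 days before the contraception period ends, but without exposure to active drug. Subjects who meet the case definition are called at Days 90 and 180; those calls list no pregnancy query either (sections 7.3.5 and 7.3.6).

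**Step 4. What can the Day 43 test miss while women are still on drug?** Latest conception day detected = 43 − lag.
- Lag 10 to 14 days: conceptions after Day 33 to Day 29 are missed, that is, the last 42 − 33 = 9 to 42 − 29 = 13 dosing days.
- Lag 7 to 21 days: the range is 42 − 36 = 6 to 42 − 22 = 20 dosing days.

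No later scheduled test or listed query would pick these up.

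**The case against.** The strongest reply is that the protocol already has a route to the birth outcome. Section 9.3.3 covers both arms, follows each reported pregnancy to two months after birth and records the child's health. Section 2.3.1 says that this is done to look for effects on the fetus, and section 5.3.3.1 repeats the follow-up. Section 9.3.1 opens with a 24-hour SAE reporting rule that has no end date, and its post-study clause accepts late related SAEs. Section 9.2.1 says that the product is always suspect and that doubtful cases should be reported. A site that learned of an anomaly through pregnancy follow-up could well file an SAE.

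This stands, and it rules out several stronger readings that a reader might infer:
- *That the plan cannot capture fetal harm at all.* It can, for any reported pregnancy.
- *That the SAE tables are bound to show no birth defects.* This would require the Day 49 line to override sections 9.3.1 and 9.3.3. The protocol does not say that it does; the passages conflict.
- *That pregnancies after Day 49 go unreported.* The reporting period is undefined rather than fixed at Day 49, and the provision for a pregnancy arising after database lock sits poorly with so early an end. Step 3 measures scheduled contact, not the limit of reporting.
- *That section 9.4 drops new SAEs in fluconazole recipients.* That sentence concerns subjects dismissed after Day 43, who are placebo recipients without coccidioidomycosis. The next sentence keeps fluconazole recipients to Day 49.
- *That the problem affects most of the fluconazole arm.* The arm includes men and women of all adult ages, and the number of women of childbearing potential is not given.

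The 30-day period is also a contraception requirement; the protocol does not call it a surveillance window. Women may be told to report pregnancies in the consent form or Manual of Procedures, neither of which is available here. The visit sections show only that no query is listed.

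The reply does not remove the literal conflict inside section 9.2.2, the relatedness condition on the post-study route, or the undefined reporting period.

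**Conclusion.** The point holds as an internal inconsistency with a practical consequence. The Day 49 SAE window cannot contain a birth from an on-study conception: even at the early-preterm bound, the earliest falls 106 days after it. Read literally, section 9.2.2 therefore keeps a named SAE type out of the SAE set that section 11.4.3 analyses, although an anomaly in a reported pregnancy would be known through section 9.3.3.

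Separately, about 23 of the 30 post-dose contraception days (21 to 24 across the call window, 27 if dosing ran to Day 46) have no scheduled contact for fluconazole recipients without coccidioidomycosis. Pregnancy ascertainment there relies on an unsolicited report within an undefined period. How many women this affects cannot be worked out from the protocol.

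The first result rests on the gestation assumption but is insensitive to it. The second rests on a last dose at about Day 42.

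**What to change.** 1. In sections 9.2.2 and 9.4, exempt congenital anomaly or birth defect from the Day 49 cut-off. Collect it as an SAE in both arms through the two-month post-birth follow-up already in section 9.3.3. Align the same limit in section 4. Section 11.4.3 refers back to section 9.2.2, so it then includes these events.
2. In section 9.3.3, replace 'during the study period' with 'from first dose to 30 days after last dose', which is the end point the protocol already uses for contraception.
3. At Visit 04 (both arms) and the Day 49 call, instruct women of childbearing potential to report any pregnancy in that window. A brief remote contact at its end, at about Day 72, is optional.

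The cost is protocol wording and a sentence at contacts already scheduled; no clinic visit or new test is needed. The downside is a few more pregnancies to follow and some late outcomes. A conception on Day 72 would be followed to about 72 + 266 + 60 = Day 398, so some outcomes may arrive after database lock. Section 9.3.3 already provides for supplemental reports.

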9.3. Reporting Procedures

9.3.1. Serious Adverse Events

Any AE that meets a protocol-defined serious criterion must be submitted immediately (within 24 hours of site awareness) on an SAE form to the DMID Pharmacovigilance Group, at the following address:

**DMID Pharmacovigilance Group
Clinical Research Operations and Management Support (CROMS)
[name]
[name], USA
SAE Hot Line: [name] (US) or [name] (outside US)
SAE [contact] (US) or [name] (outside US)
SAE Email Address: [contact]**

In addition to the SAE form, selected SAE data fields must also be entered into AdvantageEDC. Please see the protocol-specific MOP for details regarding this procedure.

Other supporting documentation of the event may be requested by the DMID Pharmacovigilance Group and should be provided as soon as possible.

The DMID Medical Monitor and DMID Clinical Project Manager will be notified of the SAE by the DMID Pharmacovigilance Group. The DMID Medical Monitor will review and assess the SAE for regulatory reporting and potential impact on study subject safety and protocol conduct. At any time after completion of the study, if the site principal investigator or appropriate sub-investigator becomes aware of an SAE that is suspected to be related to study product, the site principal investigator or appropriate sub-investigator will report the event to the DMID Pharmacovigilance Group.

9.3.2. Regulatory Reporting for Studies Conducted Under DMID-Sponsored IND

Following notification from the site principal investigator or appropriate sub-investigator, DMID, the Investigational New Drug (IND) sponsor, will report any suspected adverse reaction that is both serious and unexpected. DMID will report an adverse event as a suspected adverse reaction only if there is evidence to suggest a causal relationship between the drug and the adverse event. DMID will notify FDA and all participating site principal investigators (i.e., all principal investigators to whom the sponsor is providing drug under its IND(s) or under any principal investigator's IND(s)) in an IND safety report of potential serious risks from clinical trials or any other source, as soon as possible, but in no case later than 15 calendar days after the sponsor determines that the information qualifies for reporting as specified in 21 CFR Part 312.32. DMID will also notify FDA of any unexpected fatal or life-threatening suspected adverse reaction as soon as possible, but in no case later than 7 calendar days after the sponsor's

initial receipt of the information. Relevant follow-up information to an IND safety report will be submitted as soon as the information is available. Upon request from FDA, DMID will submit to FDA any additional data or information that the agency deems necessary, as soon as possible, but in no case later than 15 calendar days after receiving the request.

All serious events designated as “not related” to study product(s) will be reported to the FDA at least annually in a summary format.

